
Population
	
 Vision Cohort 3: Ultra-Low Vision Visual Functioning Questionnaire (ULV-VFQ-50), and PROMIS®-29, MRDQ and ViSIO-PRO 
Key Eligibility Criteria: The entire list of eligibility criteria is in section 2.3.1 and must be reviewed at the Screening Visit. All eligibility criteria must be met to enroll into the genetic screening phase. A key subset of those eligibility criteria includes the following.
 
 Age \geq 18 years of age Clinical diagnosis of retinal dystrophy Must meet one of the Genetic Screening Criteria: 
 Screening Group A: At least 2 disease-causing variants in the EYS gene which are homozygous or heterozygous in trans, based on a report from a clinically-certified lab (or a report from a research lab that has been pre-approved by the study Genetics Committee) Screening Group B: Only 1 disease-causing variant in the EYS gene, based on a report from a clinically-certified lab (or a report from a research lab which has been pre-approved by the study Genetics Committee) Screening Group C: At least 2 disease-causing variants in the EYS gene which are unknown phase, based on a report from a clinically-certified lab (or a report from a research lab which has been pre-approved by the study Genetics Committee) 
Participants eligible upon initial screening will continue to the genetic screening phase. Following the genetic screening phase, to be eligible to enroll in the study cohort, the following must be documented:
 
 Final Study Cohort Criteria: At least 2 disease-causing variants in the EYS gene which are homozygous or heterozygous in trans, based on a report from a clinically-certified lab (or a report from a research lab that has been pre-approved by the study Genetics Committee), and confirmed by a Central Genetics Auditor (CGA). 												

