 162 consent process
- 163 2. Ability to return for all study visits over 48 months
- 164 3. Age \geq 18 years
- 165 4. Must meet one of the Genetic Screening Criteria, defined below:
- 166 • **Screening Group A:** At least 2 disease-causing variants in the *EYS* gene which
 167 are **homozygous** or **heterozygous in trans**, based on a report from a clinically-
 168 certified lab (or a report from a research lab that has been pre-approved by the
 169 Genetics Committee)
 - 170 • **Screening Group B:** Only 1 disease-causing variant in the *EYS* gene, based on
 171 a report from a clinically-certified lab (or a report from a research lab which has
 172 been pre-approved by the Genetics Committee)
 - 173 • **Screening Group C:** At least 2 disease-causing variants in the *EYS* gene which
 174 are **unknown phase**, based on a report from a clinically-certified lab (or a report
 175 from a research lab which has been pre-approved by the Genetics Committee)

176

177 *Note pertaining to all Screening Groups: if a participant has a variant(s) of unknown*
 178 *significance, he/she would still qualify as long as there is at least 1 disease-causing variant(s) on*
 179 *the EYS gene.*

180

181 Participant Exclusion Criteria

182 Participants must not meet any of the following exclusion criteria at the Screening Visit in order
 183 to be eligible to *enroll into the genetic screening phase*.

- 184 1. Mutations in genes that cause autosomal dominant retinitis pigmentosa (ADRP), X-
185 linked retinitis pigmentosa (RP), or presence of biallelic mutations in autosomal
186 recessive RP/retinal dystrophy genes other than *EYS*
187 2. Expected to enter experimental treatment trial at any time during this study
188 3. History of more than 1 year of cumulative treatment, at any time, with an agent
189 associated with pigmentary retinopathy (including hydroxychloroquine, chloroquine,
190 thioridazine, and deferoxamine)
191

192 **2.3.1.2 Ocular Criteria**

193 Ocular Inclusion Criteria

194 Both eyes must meet all of the following at the Screening Visit in order for a participant to be
195 eligible to ***enroll into the genetic screening phase.***

- 196 1. Clinical diagnosis of retinal dystrophy
197 2. Clear ocular media and adequate pupil dilation to permit good quality photographic
198 imaging
199

200 Ocular Exclusion Criteria

201 If either eye has any of the following at the Screening Visit, the participant is not eligible to

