202 ***enroll into the genetic screening phase.***

- 203 1. Current vitreous hemorrhage
204 2. Current or any history of rhegmatogenous retinal detachment
205 3. Current or any history of (e.g., prior to cataract or refractive surgery) spherical
206 equivalent of the refractive error worse than -8 Diopters of myopia
207 4. History of intraocular surgery (e.g., cataract surgery, vitrectomy, penetrating
208 keratoplasty, or LASIK) within the last 3 months
209 5. Current or any history of confirmed diagnosis of glaucoma (e.g., based on
210 glaucomatous VF changes or nerve changes, or history of glaucoma filtering surgery)
211 6. Current or any history of retinal vascular occlusion or proliferative diabetic
212 retinopathy
213 7. History or current evidence of ocular disease that, in the opinion of the investigator,
214 may confound assessment of visual function
215 8. History or evidence of active treatment for retinitis pigmentosa that could affect the
216 progression of retinal degeneration, including:
217 a. Any use of ocular stem cell or gene therapy
218 b. Any treatment with ocriplasmin
219 c. Treatment with an ophthalmic oligonucleotide within the last 9 months (last
220 treatment date is less than 9 months prior to Screening Visit date)
221 d. Treatment with any other product within five times the expected half-life of
222 the product (time from last treatment date to Screening Visit date is at least 5
223 times the half-life of the given product)
224

225 **2.3.2 Screening Data Collection and Testing**

226 The study design schematic at the beginning of the protocol shows the flow of the Screening
 227 Visit. The following procedures will be performed at the Screening Visit. The testing
 228 procedures are detailed in the Pro-EYS Procedures Manuals. An overview of the equipment and
 229 technician requirements for all testing is in section 3.4. All ocular testing will be performed in
 230 each eye, right eye (OD) first and then left eye (OS).

231 Participants meeting criteria to continue will be *enrolled into the genetic screening phase*
 232 (section 2.4). Otherwise, the participant will be an *initial screen failure* (section 2.3.3). The
 233 below information will be collected at the Screening Visit:

- 234 1. Contact information (retained at the clinical site and not entered into study database)
- 235 2. Inclusion and exclusion criteria assessment (criteria in sections 2.3.1.1 and 2.3.1.2)
- 236 3. Demographics (including sex, race, ethnicity)

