- 237 4. A medical history will be elicited from the study participant and extracted from available
 238 medical records, including patient-reported daily activities, pre-existing medical
 239 conditions and medications
- 240 5. Complete ophthalmic exam. Exam will include slit-lamp biomicroscopy, indirect
 241 ophthalmoscopy, and intraocular pressure (IOP). IOP measurements will be taken prior
 242 to pupil dilation
- 243 6. Genetic screening assessment (including number and phase of mutations in the *EYS* gene,
 244 history of consanguinity, and collection of the source genetic report(s) available at the
 245 clinical site)
 - 246 ➤ This includes an assessment that the participant meets one of the Genetic Screening
 247 Criteria described in section 2.3.1.1. If the participant does not meet the criteria for
 248 one of the Genetic Screening Groups (section 2.3.1.1), the remainder of procedures
 249 and testing are not required. Participant should be discontinued as an *initial screen*
 250 *failure* per section 2.3.3
- 251 7. Visual acuity (including refraction, ETDRS, BRVT if needed, LLVA if needed)
 - 252 ➤ The VA letter score will determine whether LLVA or BRVT should be performed.
 253 The criteria are defined in the Pro-EYS Procedures Manuals.
- 254 8. Kinetic VF III4e (or historical measurement performed within the last 18 months prior to
 255 or including the Screening Visit date) Vision Cohort determination, based on eye with
 256 better visual acuity and kinetic VF above (criteria in section 2.1.1)
 - 257 ➤ If the participant’s determined Vision Cohort is closed for enrollment, the remainder
 258 of procedures and testing are not required. Participant should be discontinued as an
 259 *initial screen failure* per section 2.3.3

260

261 **2.3.3 Initial Screen Failures**

262 Participants who do not meet criteria to continue as noted above will be discontinued as an *initial*
 263 *screen failure*. The Screening Visit Form will still be completed, entering “Not Done” for

264 testing not finished. A Final Status Form will be completed, and the reason for screen failure
 265 will be noted.

266

267 **2.4 Genetic Screening Phase**

268 Participants passing the initial screening and enrolling into the Genetic Screening Phase will
 269 complete the following genetic testing and/or review procedures, according to their Screening
 270 Group (defined in section 2.3.1.1). The study design schematic at the beginning of the protocol

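### Ocular exclusion 8d states its five-half-life washout in one direction in the sentence and in the opposite direction in the parenthesis

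*Protocol*

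**What the plan says.** The ocular exclusion list in Protocol section 2.3.1.2 opens with the rule that governs every item in it: "If either eye has any of the following at the Screening Visit, the participant is not eligible to" enter genetic screening. Meeting an item therefore excludes.

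Item 8 concerns prior therapy: "History or evidence of active treatment for retinitis pigmentosa that could affect the" course of the degeneration. Its last two sub-items are time limits, each with an explanatory parenthesis:

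- **8c** excludes ophthalmic oligonucleotide treatment in the preceding 9 months. Its parenthesis says the last "treatment date is less than 9 months prior to Screening Visit date".
- **8d** covers everything else: "Treatment with any other product within five times the expected half-life of" the product. Its parenthesis says "the product (time from last treatment date to Screening Visit date is at least 5" times the half-life.

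The list is operative. The Protocol Summary, under Population, states: "The entire list of eligibility criteria is in section 2.3.1 and must be reviewed at the Screening Visit". Section 2.3.2 makes this a Screening Visit task: "Inclusion and exclusion criteria assessment (criteria in sections 2.3.1.1 and 2.3.1.2"). The key criteria repeated in the Protocol Summary do not include item 8, so 8d appears only once.

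**The concern.** An exclusion criterion should yield one answer for a given candidate. Item 8d yields two, because its parenthesis describes the people its sentence leaves eligible. A reader who has just read 8c, where the parenthesis restates the exclusion, will expect the same in 8d and find the opposite.

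Two misreadings are possible at a site:

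- Taking the parenthesis as the exclusion refuses people who have completed the washout.
- Applying both halves as exclusions refuses anyone ever treated for retinitis pigmentosa with a product outside 8a to 8c, whatever the date.

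About 30 sites worldwide will apply the item (section 2.1), and section 1.4 counts uniform definitions of treatments across sites among the measures against bias. Needless refusals are also unwelcome in a rare disease. Section 2.1.1 sets a goal of 90 participants in Vision Cohorts 1 and 2 combined and a floor of 65 should recruitment lag.

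**Working it through.** No figure in the protocol depends on this item, so the check is a logical one. Let *t* be the time from last treatment to the Screening Visit and *h* the half-life of the product.

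**Step 1. Direction of each clause, read as an exclusion under the list's opening rule**

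| Item | Main clause excludes if | Parenthesis states | Same direction? |
|---|---|---|---|
| 8c | *t* < 9 months | *t* < 9 months | yes |
| 8d | *t* < 5*h* | *t* ≥ 5*h* | no, exact complement |

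**Step 2. Test values for 8d**

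| *t* | Main clause met? | Parenthesis met? |
|---|---|---|
| 2*h* | yes | no |
| 10*h* | no | yes |

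No value of *h* reconciles the two. If both are applied as exclusions, the condition is *t* < 5*h* or *t* ≥ 5*h*, which is true for every *t*. Everyone with such a history would be refused.

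**Step 3. What the parenthesis would exclude.** Assume first-order elimination; the protocol states no kinetics. The fraction of the last dose remaining after *k* half-lives is 0.5^*k*. At *k* = 5 this is 0.5^5 = 0.03125, or 3.1%. Anyone meeting the parenthesis has at most that much left, so on this assumption refusing them serves no washout purpose.

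**Step 4. Illustration.** The protocol names no product for 8d, so take an assumed half-life of 7 days. The limit is 5 × 7 = 35 days. A candidate last treated 60 days before screening is 60 / 7 = 8.57 half-lives out, with 0.5^8.57 = 0.26% remaining. The main clause does not exclude this person, but the parenthesis describes them. For assumed half-lives from 1 to 30 days the limit runs from 5 to 150 days, and the conflict is the same at each value.

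**Step 5. Other text that might settle it.** No other part of the protocol restates or corrects 8d.

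**The case against.** The strongest reply is that the rule is not really in doubt. The main clause states the exclusion, the stem of item 8 is about active treatment, and 8c shows the pattern. A site that followed only the parenthesis would turn away people treated long ago and accept people still on drug, which defeats the purpose of the item. The parenthesis might also be a clumsy statement of the washout needed to qualify, which gives the same rule as the main clause. On this view the harm is speculative: it requires a site to put the parenthesis above the sentence it explains, or to apply two complementary halves together. The number of candidates affected is unknown and may be zero.

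Much of this stands. The intent can be inferred, the effect is unquantified, and the half-life figures above only illustrate a point that is purely logical. People treated recently are still caught by the main clause and the stem, so there is no case here that they would be admitted or that estimated progression rates would be biased.

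It does not remove the error. The text nowhere signals that the parenthesis states an eligibility condition, and it sits in a list of exclusions directly below a parenthesis that restates its own exclusion. Even on the charitable reading, two adjacent parentheses run in opposite directions without warning. That the intent can be worked out makes the point minor, but the criterion still needs correcting.

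**Conclusion.** The point holds as a minor wording correction. As written, the two halves of 8d contradict each other in an eligibility criterion that sites must apply.

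The consequence is confined to candidates previously treated for retinitis pigmentosa with a product outside 8a to 8c. The likeliest error is an unnecessary refusal. The size cannot be estimated from the protocol and is probably small. Sample size, power and planned analyses are unaffected.

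The contradiction itself rests on no numerical assumption. Only the remark that refusal would serve no washout purpose depends on first-order elimination. The conclusion about intent rests on the main clause, the stem of item 8 and the parallel with 8c.

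**What to change.** In the parenthesis of 8d, replace *at least* with *less than*, so that the condition is fewer than five half-lives since last treatment. It then agrees with its sentence and follows the form of 8c.

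Check the eligibility form, which is not part of the protocol, and correct it if it carries the same wording.

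If screening has begun, recheck candidates with this treatment history. Initial screen failures matter most, since wrongful refusal is the plausible error. They can be traced because section 2.3.3 provides that "A Final Status Form will be completed, and the reason for screen failure" is noted there.

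The cost is one phrase in the protocol, one form check and a review of any screen failures recorded under item 8.

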3.1 Baseline Visit

339 Participants meeting criteria to enter the natural history study (section 2.5) will return for a
 340 Baseline Visit date within 90 days of the Screening Visit date if possible, and no later than 2
 341 weeks after receiving confirmation of meeting *final study cohort criteria* from the CGA. The
 342 Baseline Visit date is the date on which the Baseline Visit testing procedures begin. All Baseline
 343 Visit testing procedures should be completed within 7 days of the Baseline Visit date, except
 344 PROs as specified below.
 345

346 The testing performed at the Screening Visit will serve as baseline measures for the study and
 347 will not be completed again at the Baseline Visit. The only exception is if Baseline Visit date is
 348 more than 90 days after Screening Visit date, then visual acuity testing will be repeated
 349 (including refraction, ETDRS, LLVA if needed, BRVT if needed).
 350

3.2 Baseline Testing Procedures

352 The following procedures will be performed at the Baseline Visit. The testing procedures are
 353 detailed in the Pro-EYS Procedures Manuals. **An overview of the equipment and certification
 354 requirements for all testing is in section 3.4.** All ocular testing will be performed in each eye,
 355 OD first and then OS.

- 356 1. Medical updates, including new/changed adverse events, ocular procedures, and
 357 medications
- 358 2. Physical exam (including height, weight, and blood pressure)
- 359 3. Patient Reported Outcomes (PROs)- may be completed in person or remotely (phone or
 360 other remote methods) any time within 6 months of the Baseline visit)
 - 361 a. VA LV VFQ-48 - *Vision Cohorts 1 and 2 only*
 - 362 b. ULV-VFQ-50 - *Vision Cohort 3 only*
 - 363 c. PROMIS®-29 - *All Vision Cohorts*
 - 364 d. MRDQ- *All Vision Cohorts*
 - 365 e. ViSIO-PRO- *All Vision Cohorts*
- 366 4. Contrast sensitivity - *Vision Cohorts 1 and 2 only*
- 367 5. SD-OCT
- 368 6. Axial Length and Corneal Curvature measurements
- 369 7. Near Infrared Reflectance Photos
- 370 8. Fundus Autofluorescence (on Optos, *where available*)
- 371 9. Fundus Autofluorescence (on Heidelberg Spectralis, *where available*)
- 372 10. Full-field ERG -*Vision Cohorts 1 and 2 only*

373 a. If non-detectable in the past (defined at investigator discretion), testing is not
 374 required

375 11. Full-field Stimulus Threshold

376 12. Static perimetry - *Vision Cohorts 1 and 2 only*

- 377 a. Two tests will be performed. The clinical site will compare the certified
 378 technician-determined mean sensitivity from test 1 versus test 2
- 379 ○ If the absolute value of the difference between the two tests is ≤ 2.4 dB then
 380 the participant passes static perimetry reliability criteria and a third test is not
 381 needed
 - 382 ○ If the absolute value of the difference between the two tests is > 2.4 dB then
 383 the participant does not pass static perimetry reliability criteria, and a third test
 384 is needed

385 13. Fundus-guided microperimetry- *Vision Cohorts 1 and 2 only*

- 386 a. Two tests will be performed. The clinical site will compare the certified
 387 technician-determined mean sensitivity from test 1 versus test 2
- 388 ○ If the absolute value of the difference between the two tests divided by the
 389 average between them is $\leq 50\%$ OR the absolute value of the difference
 390 between the two tests is ≤ 0.5 dB, then the participant passes microperimetry
 391 reliability criteria and a third test is not needed
 - 392 ○ If the absolute value of the difference between the two tests divided by the
 393 average between them is $> 50\%$ AND the absolute value of the difference
 394 between the two tests is > 0.5 dB then the participant does not pass
 395 microperimetry reliability criteria and a third test is needed

396

397 **3.3 Follow-up Visits**

398 The Baseline Visit date is considered study day 0, from which follow-up visit windows are
 399 timed. The Follow-up Visit date will be the date the Follow-up Visit testing procedures started.
 400 All Follow-up Visit testing procedures should be completed on the same date, with the exception
 401 of PROs, which can be completed ± 6 weeks of the required visits as noted below.

402

403 Follow up visits will be conducted at:

Visit	Target	Target Window	Allowable Window
12 Month Visit (Vision Cohorts 1 and 2)	52 Weeks	± 4 Weeks	± 6 Weeks
24 Month Visit (Vision Cohorts 1 and 2)	104 Weeks	± 4 Weeks	± 6 Weeks
36 Month Visit (Vision Cohorts 1 and 2)	156 Weeks	± 4 Weeks	± 6 Weeks
48 Month Visit (All Vision Cohorts)	208 Weeks	± 4 Weeks	± 6 Weeks

404

405 Visits should be scheduled in the target window whenever possible. If circumstances do not
 406 permit this, visits may be scheduled to extend out to the allowable window without being

407 considered a protocol deviation, but the reason for scheduling outside of the target window will
 408 be documented on the visit form. Visits occurring out of the allowable window may still be
 409 completed and used for analysis but will be documented as protocol deviations. Details
 410 regarding when to consider a visit missed are specified in the Pro-EYS Procedures Manuals.

411
 412 The goal will be for all participants to complete all scheduled visits. However, participants who
 413 (because of unforeseen circumstances) are unable or unwilling to return for all follow-up visits
 414 will be permitted to return for key visits only as an alternative to withdrawal from the study. When
 415 a participant is placed into this status, missed visits will not be recorded as protocol deviations
 416 (since they would not be recorded as protocol deviations if the participant was dropped from the
 417 study).

418
 419

420 **3.3.1 Follow-up Visit Testing Procedures**

421 The following procedures will be performed at the Follow-up Visits as noted below. The testing
 422 procedures are detailed in the Pro-EYS Procedures Manuals. An overview of the equipment and
 423 certification requirements for all testing is in section 3.4. All ocular testing will be performed in
 424 each eye, OD first and then OS.

425

426 Vision Cohorts 1 and 2

427 The following will be performed at the 12 Month, 24 Month, 36 Month, and 48 Month Visits
 428 unless otherwise noted.

- 429 1. Medical updates, including new/changed AEs, ocular procedures, and medications
- 430 2. Patient Reported Outcomes (VA LV VFQ-48, PROMIS®-29, MRDQ, ViSIO-PRO) – *24*
 431 *Month and 48 Month Visits only*
 - 432 a. May be completed in person or remotely (phone or other remote methods) any
 433 time within the Allowable Window of the associated visit
- 434 3. Complete ophthalmic exam. Exam will include slit-lamp biomicroscopy, indirect
 435 ophthalmoscopy, and intraocular pressure (IOP). IOP measurements will be taken prior
 436 to pupil dilation
- 437 4. Visual acuity (including refraction, ETDRS, BRVT if needed, LLVA if needed)
 - 438 a. The visual acuity letter score will determine whether LLVA or BRVT should be
 439 performed. The criteria are defined in the Pro-EYS Procedures Manuals.
- 440 5. Contrast sensitivity
- 441 6. SD-OCT
- 442 7. Fundus Autofluorescence (on Optos, *where available*)
- 443 8. Fundus Autofluorescence (on Heidelberg Spectralis, *where available*)
- 444 9. Full-field ERG - *48 Month Visit only*
- 445

446 a. If ERG was non-detectable prior to or at baseline (defined at investigator
447 discretion), testing is not required

448 10. Full-field Stimulus Threshold

449 11. Static perimetry

450 a. Static perimetry should be completed to the best of the participant's ability. If the
451 investigator feels that the participant will be unable to complete static perimetry
452 reliably at the follow up visit, a waiver may be obtained in advance from the study
453 chair to skip static perimetry

454 12. Fundus- guided Microperimetry

455 a. Fundus- guided microperimetry should be completed to the best of the
456 participant's ability. If the investigator feels that the participant will be unable to
457 complete microperimetry reliably at the follow up visit, a waiver may be obtained
458 in advance from the study chair to skip microperimetry

459

460 Vision Cohort 3

461 The following will be performed at the 48 Month Visit.

462 1. Medical updates, including new/changed adverse events, ocular procedures, and
463 medications

464 2. Patient Reported Outcomes (ULV-VFQ-50, PROMIS®-29, MRDQ and ViSIO-PRO)

465 a. May be completed in person or remotely (phone or other remote methods) any
466 time within the Allowable Window of the associated visit

467

468 3. Complete ophthalmic exam. Exam will include slit-lamp biomicroscopy, indirect
469 ophthalmoscopy, and intraocular pressure (IOP). IOP measurements will be taken prior
470 to pupil dilation

471 4. Visual acuity (including refraction, ETDRS, BRVT if needed, LLVA if needed)

472 a. The visual acuity letter score will determine whether LLVA or BRVT should be
473 performed. The criteria are defined in the Pro-EYS Procedures Manuals.

474 5. SD-OCT

475 6. Fundus Autofluorescence (on Optos, *where available*)

476 7. Fundus Autofluorescence (on Spectralis, *where available*)

477 8. Full-field Stimulus Threshold

478

479 Phone contact will be scheduled at 12, 24, and 36 Month intervals. The purpose of the phone
480 contact will be to keep the participants engaged in the study during the interim between the
481 Baseline and 48 Month Follow-up Visits and keep contact information updated. Changes in
482 medications and AEs will also be collected.

483

484 **3.3.2 Unscheduled Visits**

485 Testing procedures at unscheduled visits are at investigator discretion. However, it is
486 recommended that procedures that are performed should follow the standard protocol for each
487 procedure and by certified personnel whenever possible. Unscheduled visits which occur during
488 the study should be recorded in the FFB Consortium study website. Study images taken during
489 any unscheduled visits are not required to be submitted to the study website.

490

491 **3.4 Personnel and Equipment Requirements for Study Procedures**

492 The testing procedures are detailed in the Pro-EYS Procedures Manuals. An overview of the
 493 equipment and certification requirements for all testing are as follows.

Study Procedures	Equipment Required (if applicable)	Who can Perform
Investigator taking overall responsibility for a visit: oversees that consent process was performed in accordance with IRB/EC requirements, signs off on all eCRFs for a participant, eCRF edits, and protocol deviations	N/A	Certified investigator
Coordinator taking responsibility for the visit: oversees the data entry aspect of the visit, addresses protocol queries and signs off on deviations	N/A	Certified coordinator
Informed consent: explanation/review of study with the potential participant and/or signature of ICF	N/A	Certified investigator/coordinator as permitted by the IRB/EC
Signature of Informed Consent Form	N/A	Certified investigator/ coordinator as permitted by the IRB/EC
Data entry on study website	N/A	Certified coordinator (or certified investigator with additional study website certification)
Sample collection and shipping	Study will provide necessary materials – detailed in Pro-EYS Procedures Manuals	Certified coordinator
Collect information regarding medical history, demographics, physical exam, adverse events, medications	N/A	Does not need to be performed by study certified personnel*
Patient Reported Outcomes	Study will provide necessary materials – detailed in Pro-EYS Procedures Manuals	Certified coordinator
Ocular Exam (including slit-lamp biomicroscopy, indirect ophthalmoscopy and intraocular pressure IOP)	Any equipment is acceptable	Does not need to be performed by study certified personnel*
Visual Acuity - Refraction	N/A	Clinical site personnel certified for refraction
Visual Acuity - ETDRS	EVA system (preferred) otherwise ETDRS charts	Clinical site personnel certified for ETDRS
Visual Acuity - LLVA	EVA system (preferred) otherwise ETDRS charts 2.0 neutral density filter to be provided by study	Site personnel certified for performing ETDRS is also certified to perform LLVA
Visual Acuity - BRVT	BRVT charts provided by study	Clinical site personnel certified for BRVT

Contrast Sensitivity	VectorVision CSV-1000E provided by study	Does not need to be performed by study certified personnel*
SD-OCT	Heidelberg Spectralis	Clinical site personnel certified for SD-OCT
Axial Length and Corneal Curvature	Any equipment is acceptable	Does not need to be performed by study certified personnel*
Near Infrared Reflectance Photos	Heidelberg Spectralis	Clinical site personnel certified for Near Infrared Photos
Fundus Autofluorescence (on Optos)	Optos (where available)	Clinical site personnel certified for Fundus Autofluorescence on Optos
Fundus Autofluorescence (on Heidelberg Spectralis)	Heidelberg Spectralis (where available)	Clinical site personnel certified for Fundus Autofluorescence on Spectralis
Full-field ERG	Diagnosys Espion (preferred)	Clinical site personnel certified for ERG
FST	Diagnosys Espion (where available)	Does not need to be performed by study certified personnel*
Static Perimetry	Octopus 900 Pro (GATE Protocol)	Clinical site personnel certified for SP
Fundus-guided Microperimetry	MAIA (if available)	Clinical site personnel certified for MP
Kinetic Perimetry (historical)	Any equipment is acceptable	(Historical) Does not need to be performed by study certified personnel or recorded in the Pro-EYS Study Staff Delegation Log

* Personnel who will be performing procedure must be documented in the Pro-EYS Study Staff Delegation Log. The Principal Investigator (PI) is responsible for verifying individual qualifications and training specific to performing each type of procedure and ultimate accuracy and integrity of such data
		

495 **Chapter 4: Unanticipated Problem and Adverse Event Reporting**

496 **4.1 Unanticipated Problems**

497 Site investigators will promptly report to the CC all unanticipated problems meeting the criteria
 498 below. For this protocol, an unanticipated problem is an incident, experience, or outcome that
 499 meets all of the following criteria:

- 500 • Unexpected (in terms of nature, severity, or frequency) given (a) the research procedures
 501 that are described in the protocol related documents, such as the IRB/EC-approved
 502 research protocol and informed consent document; and (b) the characteristics of the
 503 subject population being studied
- 504 • Related or possibly related to participation in the research (possibly related means there is
 505 a reasonable possibility that the incident, experience, or outcome may have been caused
 506 by the procedures involved in the research)
- 507 • Suggests that the research places participants or others at a greater risk of harm than was
 508 previously known or recognized (including physical, psychological, economic, or social
 509 harm)

510 The CC also will report to the IRB all unanticipated problems not directly involving a specific
 511 site such as unanticipated problems that occur at the CC or at another participating entity such as
 512 a laboratory.

513 **4.2 Adverse Events**

514 **4.2.1 Definition**

515 Adverse Event (AE): Any untoward or unfavorable medical occurrence in a human subject,
 516 including any abnormal sign (for example, abnormal physical exam or laboratory finding),
 517 symptom, or disease, temporally associated with the subject’s participation in the research,
 518 whether or not considered related to the subject’s participation in the research (modified from the
 519 definition of AEs in the Integrated Addendum to ICH E6 (R2)).¹⁹

520

521 Serious Adverse Event (SAE): Any untoward medical occurrence that:

- 522 • Results in death
- 523 • Is life-threatening; (a non-life-threatening event which, had it been more severe, might
 524 have become life-threatening, is not necessarily considered a SAE)
- 525 • Requires inpatient hospitalization or prolongation of existing hospitalization
- 526 • Results in persistent or significant disability/incapacity or substantial disruption of the
 527 ability to conduct normal life functions (sight threatening)
- 528 • Is a congenital anomaly or birth defect

- 529 • Is considered a significant medical event by the investigator based on medical judgment
- 530 (e.g., may jeopardize the participant or may require medical/surgical intervention to
- 531 prevent one of the outcomes listed above)

532

533 **4.2.2 Reportable Adverse Events**

534 For this protocol, a reportable AE includes all events meeting the definition of an AE above.

535 All AEs—whether volunteered by the participant, discovered by study personnel during
 536 questioning, or detected through examination, laboratory test, or other means—will be reported
 537 on an AE form online.

538 The purpose of AE collection for the Pro-EYS study will be to provide historical controls for
 539 future clinical trials. As a no greater than minimal risk study, AEs do not require any specific
 540 reporting to regulatory or oversight bodies. Each Principal Investigator is responsible for abiding
 541 by any other reporting requirements specific to his/her IRB or equivalent ethics oversight
 542 committee.

543 **4.2.3 Relationship of Adverse Event to Study Procedure**

544 The study investigator will assess the relationship of any AE to be related or unrelated to a study
 545 procedure by determining if there is a reasonable possibility that the AE may have been caused
 546 by the procedure.

547 To ensure consistency of AE causality assessments, investigators should apply the following
 548 general guideline when determining whether an AE is related:

549 Yes

550 There is a plausible temporal relationship between the onset of the AE and a study procedure,
 551 and the AE cannot be readily explained by the participant’s clinical state, intercurrent illness, or
 552 concomitant therapies; and/or the AE follows a known pattern of response to a study procedure;
 553 and/or the AE abates or resolves upon discontinuation of a study procedure and, if applicable,
 554 reappears upon re-challenge.

555 No

556 Evidence exists that the AE has an etiology other than a study procedure (e.g., preexisting
 557 medical condition, underlying disease, intercurrent illness, or concomitant medication); and/or
 558 the AE has no plausible temporal relationship to a study procedure.

559 **4.2.4 Severity (Intensity) of Adverse Event**

560 The severity (intensity) of an AE will be rated on a three-point scale: (1) mild, (2) moderate, or
 561 (3) severe. A severity assessment is a clinical determination of the intensity of an event. Thus, a
 562 severe AE is not necessarily serious. For example, itching for several days may be rated as
 563 severe, but may not be clinically serious.

- 564 1. MILD: Usually transient, requires no special treatment, and does not interfere with the
- 565 participant’s daily activities

- 566
567
568
2. MODERATE: Usually causes a low level of inconvenience, discomfort or concern to the participant and may interfere with daily activities but is usually ameliorated by simple therapeutic measures and participant is able to continue in study
- 569
570
571
572
573
3. SEVERE: Interrupts a participant's usual daily activities, causes severe discomfort, may cause discontinuation of study drug, and generally requires systemic drug therapy or other treatment

574

575

Chapter 5: Miscellaneous Considerations

